12.4 Annual progress report	
12.5 Temporary halt and (premature) end of study report	
13. RISK ANALYSIS	
14. REFERENCES	

LIST OF ABBREVIATIONS AND RELEVANT DEFINITIONS

AE	Adverse event	
AI	Artificial intelligence	
AIS	Acute ischemic stroke	
AMC	Amsterdam UMC, location AMC	
Amsterdam UMC	Amsterdam University Medical Centers	
AVG	General Data Protection Regulation (in Dutch: Algemene Verordening Gegevensbescherming)	
CRF	Case report form	
СТ	Computed Tomography	
EEG	Electroencephalography	
EMS	Emergency medical service	
EVT	Endovascular thrombectomy	
ER	Emergency room	
LVO	Large vessel occlusion	
METC	Medical research ethics committee (MREC); in Dutch: medisch ethische toetsingscommissie (METC)	
MRI	Magnetic Resonance Imaging	
NIHSS	National Institute of Health Stroke Scale	
NPV	Negative predictive value	
OLVG West	Onze Lieve Vrouwe Gasthuis, location Amsterdam West	
PPV	Positive predictive value	
ROC	Receiver operating characteristic	
SAE	Serious adverse event	
Sponsor	The sponsor is the party that commissions the organisation or performance of the research, for example a pharmaceutical company, academic hospital, scientific organisation or investigator. A party that provides funding for a study but does	

not commission it is not regarded as the sponsor, but referred to as a subsidising party.

- VUMC Amsterdam UMC, location VUMC
- WMO Medical Research Involving Human Subjects Act (in Dutch: Wet Medischwetenschappelijk onderzoek met mensen)

SUMMARY

RATIONALE

Large vessel occlusion (LVO) stroke causes around 30% of acute ischemic strokes (AIS) and is associated with severe deficits and poor neurological outcomes.¹⁻⁴ Endovascular thrombectomy (EVT) enormously improves the prognosis of patients with LVO stroke, but its effect is highly time-dependent. Because of its complexity and required resources, EVT can be performed in selected hospitals only. In the Netherlands, approximately half of the EVT-eligible patients are initially admitted to a hospital incapable of performing EVT, and – once it has been ascertained that a patient requires EVT – the patient needs to be transported a second time by ambulance to an EVT-capable hospital.⁵ This workflow leads to an average treatment delay of about 1 hour, which decreases the absolute chance of a good outcome of the patient by 5-15%.⁵⁻ ⁷ To solve this issue, a prehospital stroke triage instrument is needed, which reliably identifies LVO stroke in the ambulance, so that these patients can be brought directly to an EVT-capable hospital. Electroencephalography (EEG) may be suitable for this purpose, since it shows almost instantaneous changes in response to cerebral blood flow reduction.^{8,9} Moreover, significant differences between EEGs of patients with an LVO and those of suspected AIS patients with a smaller or no vessel occlusion have been found.¹⁰ A dry electrode EEG cap enables ambulance paramedics to perform an EEG in the prehospital setting, with significant reduced preparation time compared to conventional wet electrode EEG.^{11, 12} An automatic LVO-detection algorithm will be the key to reliable, simple and fast interpretation of the EEG by paramedics, enabling direct admission of suspected AIS patients to the right hospital.

HYPOTHESIS

An EEG-based algorithm, developed with artificial intelligence (AI), will have sufficiently high diagnostic accuracy to be used by ambulance paramedics for prehospital LVO detection.

OBJECTIVE

The primary objective of this study is to develop one or more novel AI-based algorithms (the AI-STROKE algorithms) with optimal diagnostic accuracy for identification of LVO stroke in patients with a suspected AIS in the prehospital setting, based on ambulant EEG data.

STUDY DESIGN

AI-STROKE is an investigator-initiated, multicenter, diagnostic test accuracy study.

STUDY POPULATION

Part A: Adult patients with a (suspected) AIS, in the prehospital setting.

Part B: Adult patients with a (suspected) AIS, in the in-hospital setting.

INTERVENTION

A single EEG measurement with a dry electrode cap (approximately 2 minutes recording duration) will be performed in each patient. In addition, clinical and radiological data will be collected. EEG data will be acquired with a CE approved portable dry electrode EEG device.

MAIN END POINTS

- Primary end point: Based on the EEG data, and using the final diagnosis established by an adjudication committee as the gold standard, one or more novel AI-based EEG algorithms (the AI-STROKE algorithms) will be developed with maximal diagnostic accuracy (i.e. area under the ROC curve; AUC) to identify patients with an LVO stroke of the anterior circulation in a population of patients with suspected AIS.
- Secondary end points:
 - AUC, sensitivity, specificity, positive predictive value (PPV) and negative predictive value (NPV) of the AI-STROKE algorithms based on ambulant EEG for diagnosis of LVO of the anterior circulation in suspected AIS patients in the prehospital setting;
 - AUC, sensitivity, specificity, PPV and NPV of existing EEG algorithms based on ambulant EEG for diagnosis of LVO of the anterior circulation in suspected AIS patients in the prehospital setting;
 - AUC, sensitivity, specificity, PPV and NPV of existing and newly developed EEG algorithms based on ambulant EEG for detection of LVO stroke of the posterior circulation, intracerebral hemorrhage, transient ischemic attack, and stroke mimics;

• Technical and logistical feasibility (e.g. in terms of EEG channel reliability) of paramedics performing ambulant EEG in patients with a suspected AIS in the prehospital setting.

NATURE AND EXTENT OF THE BURDEN AND RISKS ASSOCIATED WITH PARTICIPATION, BENEFIT AND GROUP RELATEDNESS

A single EEG will be performed in each patient. An EEG-measurement is a safe and non-invasive procedure, regularly performed in standard medical practice. The use of dry electrodes makes it possible to perform the measurement in less than five minutes. The dry electrodes will cause no to minimal discomfort, and only during the measurement. We expect no health risks, as we will use only CE marked products for performing the EEG. The treating physicians and the ambulance paramedics will not interpret the EEG recording, therefore the EEG results will not influence choices regarding diagnosis, treatment or the hospital to which the patient is presented. Deferred informed consent will be asked as soon as logistically feasible, preferably within 72 hours after arrival at the hospital or at discharge (whichever comes first). If informed consent is given, a case report form (CRF) will be filled out containing information on patient characteristics, medical history, medication use, physical and neurological examination performed by the treating physician, results of imaging studies, diagnosis and treatment as well as logistical and technical information, obtained from the patient, the treating physician and the Emergency Medical Service (EMS). There are no follow up visits. For the patient, there is no benefit of participation in the study.

1. INTRODUCTION AND RATIONALE

Acute ischemic stroke (AIS) is a major cause of death and disability worldwide.^{13, 14} Large vessel occlusion (LVO) stroke causes around 30% of AIS and is associated with more severe deficits and worse neurological outcomes than other types of AIS.¹⁻⁴ In 2015, endovascular thrombectomy (EVT) became standard treatment for patients with LVO stroke. EVT improves the chance of good functional outcome in patients with an LVO, provided it is initiated within 6 hours, or in a selected population, within 24 hours after stroke symptom onset.¹⁵⁻¹⁷ Early initiation of EVT within these time-ranges is extremely important, as each 9minute delay results in a poor functional outcome in 1 of every 100 treated patients.¹⁸ However, EVT is a complex procedure that can be performed in specialized hospitals only, so-called comprehensive stroke centers. In the Netherlands, approximately half of EVT-eligible patients are initially admitted to a hospital where this therapy is not available, and are – once it has been established that they are eligible for EVT - transferred to an EVT-capable hospital.⁵ In other countries this proportion is even higher. In the Netherlands, this interhospital transfer delays treatment with about 1 hour and leads to an decrease in the absolute chance of functional independence of the patient by 5-15%.⁵⁻⁷ Direct presentation of all suspected AIS patients to an EVT-capable hospital, however, is also not feasible, since only approximately 7% of these patients have an LVO. Therefore, a prehospital triage instrument that reliably identifies LVO stroke patients allowing direct transport to an EVT capable hospital, is much needed.

Several diagnostic tools have previously been proposed for this purpose, but none have been found suitable. Clinical scales, containing items for scoring the severity of neurological deficit, have low diagnostic accuracy.¹⁹ Ambulances equipped with an imaging system for computed tomography (CT) and CT-angiography have high diagnostic accuracy, but issues regarding safety, clinical efficacy and cost-effectiveness make broad implementation unlikely.²⁰ Electroencephalography (EEG) may be suitable for LVO-detection, since multiple studies have shown almost instantaneous changes in the EEG-signal in response to reduction of the cerebral blood flow.^{8, 9} These changes often include a decrease in higher frequencies followed by an increase in lower frequencies, and can be quantified by EEG measures based on frequency band power.²¹ Multiple studies have shown that such quantitative EEG (qEEG) measures, e.g. the delta/alpha ratio, discriminate between AIS patients and healthy controls.²²⁻²⁴ Based on functional magnetic resonance imaging data, it is also known that the functional connectivity is affected in patients with AIS.²⁵⁻²⁷ One case-control study quantified this property by EEG coherence and phase synchronization and found reduced values in both the ipsi- and contralateral hemispheres of AIS patients compared to healthy controls.²⁴ Recently, a small study performed a single EEG in suspected stroke patients and

[figure not shown]
13

showed differences in frequency band power ratios between patients with an LVO (infarct volume > 20 cc) and a smaller or no vessel occlusion. ¹⁰ These results indicate the possibility of EEG as an instrument for identification of patients with an LVO.

2. OBJECTIVES

The primary objective of this study is to develop one or more novel AI-based algorithms (the AI-STROKE algorithms) with optimal diagnostic accuracy for identification of LVO stroke in patients with a suspected AIS in the prehospital setting, based on ambulant EEG data.

The secondary objectives are:

- Assessing the diagnostic accuracy of existing EEG algorithms for identification of LVO stroke in patients with a suspected AIS in the prehospital setting;
- Improving the applicability and reliability of the dry electrode EEG cap for use in the prehospital setting;
- Assessing the logistical and technical feasibility of ambulance paramedics performing ambulant EEGs, using an improved dry electrode EEG cap, in the prehospital setting in patients with a suspected AIS.

3. STUDY DESIGN

AI-STROKE is an investigator-initiated, multicenter, diagnostic test accuracy study.

PART A: ALGORITHM DEVELOPMENT AND VALIDATION IN THE PREHOSPITAL SETTING

This part is carried out by two ambulance services (Ambulance Amsterdam and Ambulance Noord-Holland Noord). These ambulances almost exclusively transport suspected AIS patients to the following hospitals: AMC, VUMC, OLVG West and Noordwest Ziekenhuisgroep, location Alkmaar. The ambulance services and these hospitals are therefore all participating centers in this study. A single EEG will be performed in patients with a suspected AIS as assessed by the ambulance paramedic, or with a radiologically confirmed LVO (in case of transport to an EVT center). The acquired data will be used for development and validation of one or more AI-algorithms for LVO-detection and validation of existing EEG-algorithms.

PART B: ALGORITHM DEVELOPMENT AND VALIDATION IN THE EMERGENCY ROOM

This part is carried out in the emergency room (ER) of AMC. A single EEG will be performed in patients with a suspected AIS as assessed by the ambulance paramedic that presents the patient to the ER, or with a radiologically confirmed LVO and who are transported to the AMC for EVT. We will use the data for training and validation of one or more AI-algorithms for LVO-detection and validation of existing EEG-algorithms.

At the start of the study, EEG data of suspected AIS patients will be limited. In this phase, we will use existing fully anonymized EEG data, obtained as part of standard medical care, and data from the ELECTRA-STROKE study for pretraining of the AI-algorithms (see chapter 10).

In both study parts a single EEG is performed. After informed consent is given, information is collected on patient characteristics, medical history, medication use, physical and neurological examination performed by the treating physician, imaging studies, diagnosis and treatment as well as logistical and technical information, obtained from the patient, the treating physician and the Emergency Medical Service (EMS). There are no follow up visits.

Each patient will be enrolled once. If the patient has already been included in the study in the prehospital setting, no EEG will be performed in part B. The study will run until the maximum number of inclusions is reached (as specified in chapter 4.4) or earlier when the steering committee decides that an accurate and stable algorithm can be developed with the data collected up till that point. Two interim analyses will take place as described in chapter 10, at which time the steering committee may decide to prematurely stop the recruitment in the study.

16

Based on findings in our pilot ELECTRA-STROKE study, we are optimizing the EEG-hardware to improve the reliability and applicability of the dry electrode EEG cap in acute care settings. We will assess the technical and logistical feasibility of performing EEGs using the optimized EEG-hardware in patients with a suspected AIS in the ambulance.

4. STUDY POPULATION

4.1 POPULATION (BASE)

PART A

We will recruit patients with a suspected AIS or a known LVO of the anterior circulation, in the ambulance, who meet the criteria described in chapter 4.2 and 4.3.

PART B

We will recruit patients with a suspected AIS or a known LVO of the anterior circulation, presented to the ER of the AMC, who meet the criteria described in chapter 4.2 and 4.3.

4.2 INCLUSION CRITERIA

PART A AND B

All subjects must meet all of the following criteria:

- Suspected AIS, as assessed by the attending ambulance paramedic, or a known LVO stroke;
- Onset of symptoms or last seen well < 24 hours before EEG acquisition;
- Age of 18 years or older;
- Written informed consent by patient or legal representative (deferred).

4.3 EXCLUSION CRITERIA

A potential subject who meets any of the following criteria will be excluded from participation in this study (parts A and B):

- Skin defect or active infection of the scalp in the area of the electrode cap placement;

- (Suspected) COVID-19 infection.

4.4 SAMPLE SIZE CALCULATION

We aim to develop and validate a novel algorithm for diagnosis of LVO stroke. In the prehospital and inhospital setting together, EEG-measurements will be performed in a maximum of 1192 patients.

Using preliminary data of the ongoing ELECTRA-STROKE study (clinicaltrials.gov, NCT03699397), we identified two independent EEG predictors for LVO stroke: the theta-alpha ratio and the weighted phase lag index. For optimal algorithm development, using conventional statistical methods, 20-50 events (i.e. LVO strokes) per predictor are required in the derivation cohort.³⁰ Thus, with conventional statistics, 40-100 patients with an LVO stroke would be required for algorithm development. Based on an incidence of 12% for LVO stroke among patients with a suspected AIS³¹, and assuming a dropout rate of 30% (either due to missing consent or failed EEG registration), 484-1192 patients with a suspected AIS are required.

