10. ALGORITHM DEVELOPMENT AND STATISTICAL ANALYSIS

ALGORITHM DEVELOPMENT

The EEG data obtained in the prehospital setting and in the ER will be divided in a training (80%) and validation (20%) set. Only the training set will be used to train novel AI-algorithms for LVO-detection. First, we will create a logistic regression model based on standard EEG-features, e.g. time domain characteristics, power spectral density in different frequency bands, coherence measures, and entropy measures. This model will be the reference to assess the improvement of the other novel AI-based models. We plan to base the final AI-STORKE algorithm on artificial neural networks, but other EEG classification algorithms (e.g. based on support vector machines and random forests) may be explored as well.³⁴ First, we will create convolution neural networks (CNN's) using the extracted EEG-features. Subsequently, we will evaluate whether the EEG-signals contain more information than these features by creating models that analyze the time series directly. To deal with the different timescales of features in EEG-signals and their dynamic behavior, we aim to study recurrent neural networks (RNN's). Examples of such RNN's include Long Short-Term Memory (LSTM)^{35, 36}, Gated Recurrent Unit (GRU) CNN's, and Deep Belief networks (DBN's)³⁷. The first models will be built using a limited set of EEG data since data collection is part of this study. We will deal with the data sparsity using two approaches: (I) Transfer learning, we will train models for other EEG classification tasks (such as classification of stroke vs. healthy subjects or male vs. female), so that features from the time signals are trained. For this, existing fully anonymized EEG data will be used. The trained models will subsequently be used to fine-tune the classification of suspected AIS patients. (II) Reinforcement learning³⁸, and uncertainty-based learning in particular. We will update the models by feeding the data that are collected during the study. During the EEG data collection, the algorithm will be evolving, and the correct classification ratio will be improving as more data are added. The final algorithm will be considered successful if an AUC of >0.80 is reached in the validation set.

STATISTICAL ANALYSIS

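### Section 4.4 makes no allowance for the 20% validation hold-out: on the plan's own inputs 484–1192 patients give about 33–80 derivation LVO strokes, not the 40–100 they were computed from

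*Combined protocol and SAP*

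**What the plan says.** Section 4.4 opens with a double aim: "We aim to develop and validate a novel algorithm for diagnosis of LVO stroke". Its calculation covers the first half only. It takes two EEG predictors from the pilot study and the rule that "20-50 events (i.e. LVO strokes) per predictor are required in the derivation cohort", and so arrives at 40–100 LVO strokes for algorithm development. It then applies a 12% LVO share among suspected stroke patients, "assuming a dropout rate of 30% (either due to missing consent or failed EEG registration"), and concludes that "484-1192 patients with a suspected AIS are required". The upper figure is also the enrolment cap for the prehospital and in-hospital parts together. Section 3 makes it the end of recruitment: "The study will run until the maximum number of inclusions is reached (as specified in chapter 4.4"), unless the steering committee stops earlier.

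Chapter 10 says that the data from both settings "will be divided in a training (80%) and validation (20%) set", and adds: "Only the training set will be used to train novel AI-algorithms for LVO-detection". Success is judged on the held-out part: "The final algorithm will be considered successful if an AUC of >0.80 is reached in the validation set".

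Sections 3, 4.1 and 4.2 also admit patients whose LVO is already known. Section 4.4 does not mention them.

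**The concern.** The events-per-predictor requirement is placed in the derivation cohort. Under chapter 10 that cohort is the 80% training set. The conversion to patients has a factor for LVO share and one for dropout, but none for the share of data that reaches training. Both ends of the published range are therefore too small for the event counts behind them.

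Two things are at stake. First, 484 is presented as a lower requirement although it does not meet the plan's own minimum. Secondly, because section 4.4 gives no expected LVO count for validation, a reader cannot see how few LVO strokes will decide the AUC criterion.

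**Working it through.** **Inputs.** From section 4.4: 20–50 events per predictor, 2 predictors, 12% LVO share, 30% dropout, 484–1192 patients. From chapter 10: 80% training, 20% validation, training set only for fitting.

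**Reproducing the plan's figures**, with N = (events / 0.12) / 0.70, rounding up at each step:

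- Upper: 2 × 50 = 100 events; 100 / 0.12 = 833.3, so 834; 834 / 0.70 = 1191.4, so 1192. This is exact.
- Lower: 2 × 20 = 40 events; 40 / 0.12 = 333.3, so 334; 334 / 0.70 = 477.1, so 478. The plan has 484, a difference of 6 patients (1.2%), which is not part of this point.

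Both ends are reached without a factor of 0.80.

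**Expected LVO strokes on the plan's inputs.** Evaluable = N × 0.70 × 0.12. Training = 0.80 of that, validation = 0.20 of that.

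| N | Evaluable | Training | Per predictor | Validation |
|---|---|---|---|---|
| 484 | 40.7 | 32.5 | 16.3 | 8.1 |
| 1192 | 100.1 | 80.1 | 40.1 | 20.0 |

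**Patients needed to have the stated events in training**, N = events / (0.80 × 0.12 × 0.70):

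- 40 events: 595.2, so 596.
- 100 events: 1488.1, so 1489, which is above the cap.

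**How far known-LVO patients could close the gap at 1192.** The overall LVO share that gives 100 training events is 100 / (1192 × 0.70 × 0.80) = 0.150, about 15%. Let x be the number of known-LVO patients, all confirmed at adjudication, with 12% LVO among the rest:

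- Same 30% dropout: (x + 0.12 × (1192 − x)) × 0.56 = 100 gives x = 40.4, so 41 patients (3.4% of 1192).
- No dropout among them: 0.80x + 0.12 × (1192 − x) × 0.56 = 100 gives x = 27.2, so 28 patients (2.3%).

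The plan gives no expected number to compare with these.

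**The case against.** The strongest reply is that nothing operational depends on the error. Recruitment is governed by 1192, which still gives 40 events per predictor and so meets the plan's own range. No stop or analysis is tied to 484. The formal reviews for early stopping come at 50 and 100 LVO patients, and if the first 50 all have consent and a usable EEG, 50 × 0.80 = 40 are in training, exactly the plan's minimum. This stands, and it limits the weight of the point.

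Other replies stand only in part:

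- *The rule is a benchmark for conventional statistics, while the final models are neural networks with pretraining.* True, but it is the only basis given for 1192, and chapter 10 also plans a logistic regression as reference model. The pretraining data come with no LVO count and are not credited in section 4.4.
- *The derivation cohort is not explicitly equated with the training set.* It is not, but chapter 10 allows only the training set for fitting, so no other reading fits as well. The interim cross-validation also runs within the training data and does not bring the hold-out back.
- *Section 8.5 lets the steering committee decide on replacement if LVO numbers are low.* That is discretionary and is not a term in the calculation.
- *Known-LVO patients may fill the gap.* They may. Some 28–41 of them would be enough, but their number is not stated, and the 12% is applied to suspected stroke only.

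A reader might infer more than the documents support: that 1192 is inadequate, that enrolment must rise to 1489, or that the study will in fact end with 80 training events. The first two fail because 40 per predictor lies inside the plan's range. The third fails because enrolment of known-LVO patients makes the realised share unknown.

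**Conclusion.** The point holds as an arithmetic omission with a modest consequence. The stated sizes do not deliver the derivation events from which they were computed; both ends are short by one fifth. The lower figure falls below the plan's minimum (16 per predictor against 20). The upper figure stays within the range (40) but misses the 50 it was built on. At the maximum, about 20 LVO strokes are expected in the set that decides success.

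This rests on the plan's 12% and 30%, on the same LVO share in both parts of the 80/20 split, and on no contribution from known-LVO patients. The counts are expectations, and an overall LVO share of about 15% would restore 100 training events at 1192.

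**What to change.** Restate section 4.4 so that sizes and event counts match, for example:

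*With the 80/20 split, a 12% LVO share and 30% dropout, 596–1192 patients are expected to give about 40–80 derivation LVO strokes (20–40 per predictor); at the maximum of 1192 about 20 LVO strokes are expected in the validation set.*

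This must replace the 484 and also the 40–100 events and 20–50 per predictor that the sizes are said to deliver. Changing 484 alone would leave 596–1192 beside 40–100, which do not correspond. The section should also say whether known-LVO patients are counted in this yield and, if so, how many are expected.

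The interim triggers should not be redefined as evaluable LVO strokes as part of this change. At 12% and 30%, 100 evaluable LVO strokes would arrive at 100 / (0.12 × 0.70) = 1190.5, about 1191 of 1192 patients, and the second look could no longer shorten recruitment.

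The cost is protocol wording, with no added enrolment. The downside is that the stated events per predictor at the maximum fall from 50 to 40.

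### The sample size rests on a 12% LVO incidence, the Introduction gives about 7% for the same named population, and the two are not reconciled: at 7%, 1192 suspected-AIS patients yield about 58 evaluable LVO strokes, not 100

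*Combined protocol and SAP*

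**What the plan says.** Section 4.4 builds the sample size in four steps.

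- Predictors: "we identified two independent EEG predictors for LVO stroke".
- Events: "20-50 events (i.e. LVO strokes) per predictor are required in the derivation cohort", and hence "40-100 patients with an LVO stroke would be required for algorithm development".
- Incidence: "Based on an incidence of 12% for LVO stroke among patients with a suspected AIS", with a citation to a prospective observational comparison of prehospital stroke scales in suspected stroke.
- Attrition: "assuming a dropout rate of 30% (either due to missing consent or failed EEG registration").

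The result is 484-1192 patients with a suspected AIS. The upper end is also the study's ceiling: "EEG-measurements will be performed in a maximum of 1192 patients".

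Section 1 gives a different share. It says "Direct presentation of all suspected AIS patients to an EVT-capable hospital, however, is also not feasible", and the reason offered is "since only approximately 7% of these patients have an LVO". No source is cited for that figure.

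Three other provisions bear on the point:

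- Section 4.2 (Inclusion criteria) also admits patients with an already known LVO stroke, and sections 3 and 4.1 say the same for both study parts. Section 4.4 makes no allowance for them.
- Section 8.5 (Replacement of individual subjects after withdrawal) lets the steering committee decide on replacement if LVO strokes are fewer than expected. It gives no number.
- Chapter 10 splits the data 80/20 into training and validation sets, and places interim analyses at 50 and 100 included LVO stroke patients.

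**The concern.** Both percentages are presented as the share of suspected-AIS patients who have an LVO, and they differ by a factor of 1.7 (12/7). Neither section ties its figure to a different LVO definition, setting or time window that would explain the gap. The protocol relies on the lower figure to argue that triage is needed and on the higher one to size the study.

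The number of LVO strokes is the effective sample size here. It limits how many parameters the training set can support, how precisely the validation AUC is estimated, and when the interim looks fall. If the Introduction's figure is nearer the truth for the patients enrolled, section 4.4 promises more LVO strokes from suspected-AIS recruitment than that recruitment would supply. PPV and NPV also depend directly on prevalence, so a reader needs to know which prevalence the plan considers relevant to intended use.

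**Working it through.** **Inputs.** Predictors 2, events per predictor 20-50, incidence 12%, dropout 30% and maximum 1192 (all section 4.4); incidence about 7% (section 1); 80/20 split and interim trigger of 100 LVO strokes (chapter 10).

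**1. Reproduce the plan's figures.** N = (events / incidence) / (1 - dropout), rounding up at each step.

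- Upper end: 100/0.12 = 833.3, so 834; 834/0.70 = 1191.4, so 1192. This matches exactly.
- Lower end: 40/0.12 = 333.3, so 334; 334/0.70 = 477.1, so 478. The plan states 484, six more, which is immaterial.

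The cap therefore comes from 12%. At 7% the same formula gives 100/(0.07 x 0.70) = 2040.8 and 40/(0.07 x 0.70) = 816.3, or about 817-2041 patients (818-2042 if rounded at each step).

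**2. Expected yield from suspected-AIS patients.** Evaluable LVO strokes = N x (1 - dropout) x incidence. For N = 1192, evaluable patients = 1192 x 0.70 = 834.4. For N = 484, they are 338.8.

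| | 12% | 7% |
|---|---|---|
| 1192 enrolled: evaluable LVO strokes | 100.1 | 58.4 |
| per predictor (divide by 2) | 50 | 29 |
| training (x 0.80) | 80.1 | 46.7 |
| validation (x 0.20) | 20.0 | 11.7 |
| 484 enrolled: evaluable LVO strokes | 40.7 | 23.7 |

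At 7% the lower end of the stated range gives about 24 LVO strokes, or 12 per predictor, below the plan's own minimum of 40 (20 per predictor). The dropout assumption does not rescue the upper target: with no dropout at all, 1192 x 0.07 = 83.4; with 40% dropout it is 50.1.

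**3. Known-LVO patients needed to restore 100.** Let k be the share of the 1192 enrolled with a known LVO, assuming that all are confirmed and that dropout is the same. Then 834.4 x [k + 0.07(1 - k)] = 100, so k = (100/834.4 - 0.07)/0.93 = 0.0536, and 0.0536 x 1192 = about 64 patients. If the interim trigger counts patients before dropout (the term is not defined), k = (100/1192 - 0.07)/0.93 = 0.0149, or about 18 patients.

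**4. Precision of the validation AUC.** By the Hanley-McNeil formula at AUC 0.80, with 167 validation patients (0.20 x 834.4), the 95% half-width is 0.120 with 20 LVO strokes and 0.153 with 12.

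**5. Prevalence and PPV, as an illustration.** PPV = p x Se / [p x Se + (1 - p)(1 - Sp)]. Specificity 0.80 is the cut-off floor in chapter 10; sensitivity 0.70 is an assumption of this review.

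- 12%: 0.084/(0.084 + 0.176) = 0.323.
- 7%: 0.049/(0.049 + 0.186) = 0.209.

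**The case against.** The best defence has four parts.

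- **The two figures are not equally supported.** The 12% is cited to a prospective study in suspected stroke. The 7% is approximate, uncited and used only in a background argument. This stands as a reason to treat 7% as a sensitivity case. It does not remove the conflict, because the documents do not say that the 7% is obsolete or refers to something else.
- **58 lies inside the plan's stated requirement of 40-100.** This also stands: 29 per predictor overall, and about 23 in training, exceed the minimum of 20. What is missed is the upper target.
- **Known-LVO patients are eligible and would add to the yield.** This stands as far as the actual count goes. They cannot justify the 12%, because section 4.4 computes on suspected-AIS patients and gives no known-LVO share.
- **Section 8.5 anticipates a shortfall.** It does, but replacement is discretionary and unquantified, and the section does not say whether 1192 may be exceeded.

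Stronger readings are tempting and are not supported. A reader might infer that the second interim analysis is unreachable. With an unknown number of known-LVO enrolments and possible replacement, that cannot be claimed. Nor do the interim triggers need to change: if the second look is not reached, recruitment simply continues to the cap. A reader might also infer that the plan overstates PPV, but it states no expected or target PPV. Finally, this is not an arithmetic error, since 1192 follows correctly from 12%.

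**Conclusion.** The point holds as an unreconciled inconsistency in a sample-size input. The documents do not show which percentage is right.

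If 7% applies, suspected-AIS recruitment to the cap gives about 42% fewer evaluable LVO strokes than section 4.4 implies (1 - 58.4/100.1). The plan's minimum is still met at the cap but not at 484 patients. The 100 that sets both the cap and the second interim look would not be reached without known-LVO enrolment or replacement.

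The figure of 58 assumes 30% dropout, no known-LVO enrolment and no replacement, so it describes suspected-AIS recruitment alone and does not forecast the whole study. The PPV figures only illustrate how far the answer depends on prevalence. They matter because known-LVO enrolment would raise the prevalence in the sample, so predictive values taken directly from it need not carry over to suspected-AIS patients.

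**What to change.** 1. Reconcile the two percentages in sections 1 and 4.4: either use one figure, or state how the two differ in population, LVO definition or source.
2. Unless that settles the matter on one figure, restate in 4.4 that 1192 suspected-AIS patients are expected to yield about 58-100 evaluable LVO strokes, of which about 47-80 fall in the training set. Show the expected known-LVO contribution as a separate line, and refer to the replacement provision in section 8.5.
3. In chapter 10, add that PPV and NPV will also be recalculated at the stated prevalence(s) from the estimated sensitivity and specificity, alongside the values observed in the sample.

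The cost is protocol wording and a less favourable stated yield. No patients are added and the interim schedule stays as it is.
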